## 13.6 IRB Review and Communications

The study protocol (CIP), informed consent form, and other study documentation forms require IRB review and approval. Communication to and from the IRB shall be directed from or to the primary Össur contact, [name], the Study Monitor. Continuous communication will be maintained between Össur and the IRB, as required. Moreover, communication will be maintained between the PI and the IRB, as required.

## 13.7 Vulnerable populations

No vulnerable populations will be enrolled.

## 13.8 Informed Consent

The Principal Investigator, or any researcher qualified, will obtain from the subject, written signed informed consent form to his/her inclusion in the study, after explaining the rationale for and the details of the study, the risks and benefits of alternative treatments, and the extent of the subject's involvement. The subject will receive a copy of the informed consent.

The subjects will be informed that their participation is voluntary and that they can withdraw from participation at any time, at his/her discretion and this will not have any consequences for the participant's treatment.

In case the information on the ICF changes, and subjects need to be provided with new information, the PI will contact each subject by phone and explain the new information as required and participants will be reconsented as applicable.

Subjects that for any reason are unable to provide informed consent will not be enrolled in the study.

## 13.9 Participant confidentiality – Data management

Subjects will be assigned a random study identification (ID) number and a random investigational device (identified by the study serial number).

When recording video care will be taken not to include the face or other identifiable features, if they are accidentally captured they will be blurred or blackened.

Confidentiality of all relevant subject feedback and information will be maintained through use of the identifying number only, in all documentation. The study sponsor, Össur, will remain the sole owner of the study data. A list connecting the ID to the subject's name will be stored in a password secured file until the end of the study at which point it will be destroyed. Only investigators involved in the trial will have access to this information.

The screening form will be in paper format and will be stored by the PI in a locked container. All documents will be collected by Study Monitor and/or PI.

A Clinical Investigation Report (CIR) will be generated by Medical Office. The report will be stored with the device technical file within Össur Quality Management System, along with the unlinked data and all accompanying investigational documents, according to the R&D and Quality documentation procedures. Subjects participating in the study can have access to the results, on demand, when the CIR is internally published.

Study results, data, and documentation will be stored for a minimum of 5 years.

## 14 Evaluation of Adverse Events and Device Deficiencies

For a list of foreseeable adverse events and anticipated adverse device effects, together with their likely incidence, mitigation or treatment see chapter 13.2 above and Hazard Analysis documentation [3].

### 14.1 Definitions of adverse events, effects and deficiencies

An adverse event (AE) is any untoward medical occurrence, unintended disease or injury, or untoward clinical signs (including abnormal laboratory findings) in subjects, users or other persons, whether or not related to the investigational medical device.

An adverse device effect (ADE) is any adverse event related to the use of an investigational medical device, including events resulting from insufficient or inadequate instructions for use, operation, malfunction, etc.

A serious/severe adverse event (SAE) is an AE that:

- Is life-threatening or fatal
- requires or prolongs hospitalization
- results in permanent impairment of a body function
- or results in permanent damage to a body structure.

A serious/severe adverse device effect (SADE) is an adverse device effect that has resulted in any of the consequences characteristic of a SAE.

An anticipated serious adverse device effect (ASADE) is an effect which by its nature, incidence, severity or outcome has been identified in the risk management for the device.

An unanticipated adverse device effect (UADE) is a serious adverse effect on health or safety of participants caused by the device if not previously identified in nature, severity, or degree of incidence in the protocol (CIP) or the risk analysis for the device.

A device deficiency (DD) is the inadequacy of a medical device with respect to its identity, quality, durability, reliability, safety or performance. Device deficiencies include malfunctions, use errors, and inadequate labelling.

A use error (UE) is an act or omission of an act that results in a different medical device response than intended by the manufacturer or expected by the user.

See ISO 14155:2011 for details.

### 14.2 Reporting procedures

Adverse events and device deficiencies are recorded and reported to the competent authority in all countries in which the trial is being conducted according to national guidelines.

All device related adverse events will be investigated. Adverse events that are serious, unanticipated and (possibly) device related shall be reported to the sponsor by telephone as soon as possible. The complete adverse event investigation form shall be faxed to the sponsor within 24 hrs. Within ten days the Sponsor will report to the IRB and the FDA. Any serious device related adverse event will lead to the immediate termination of the trial.

Participants will be provided the contact information of the investigator and told to call them in the event of an adverse event that may be connected to previous use of the device.

The Principal investigator shall supply a copy of the complete adverse event investigation form, together with a cover letter to the IRB when events are judged to be serious, unanticipated and (possibly) device related.

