## 8.7 Study monitoring and Oversight

The study monitor(s) will monitor the study to ensure all procedures are followed correctly and according to the study protocol. The study monitor will gather and review all study data and inform the PI of missing data or nonconformities to the study protocol.

The study monitor(s) and **LPI** will maintain communication on a minimum biweekly basis, via telephone and email. The **LPI** will provide the study monitor(s) with information of all scheduled study visits. The study monitor will visit the investigational site at least once while a study visit takes place.

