## 14.3 Suspension or premature termination of the clinical investigation

The sponsor/principal investigator, the IRBs, and the regulatory authorities can decide about investigation continuation. The clinical investigation can be suspended or prematurely terminated if the serious adverse device effects are considered disproportionately large compared to the possible benefits of the intervention. If the investigation is terminated or suspended all participants will be informed and appropriate follow-up will be assured. If sponsor/principal investigator terminates or suspends the investigation the relevant IRBs regulatory authorities will be provided with a detailed written explanation of the termination or suspension.

The sponsor/principal investigator can upon completion of the analysis of the reason(s) for a suspension decide to lift the suspension, when the necessary corrective actions have been implemented. The investigators, IRBs, and relevant regulatory authorities will be notified and provided with the relevant data supporting the decision.

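### The urgent telephone report to the sponsor covers only unanticipated serious device-related events, although the stopping provisions in 14.2 and 14.3 cover anticipated ones as well

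*Combined protocol and SAP*

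**What the plan says.** All section references are to the combined protocol and SAP.

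- **Telephone report (14.2).** "Adverse events that are serious, unanticipated and (possibly) device related shall be reported to the sponsor by telephone as soon as possible". Three conditions must hold together: the event is serious, it was not anticipated, and the device may have caused it.
- **Follow-on steps (14.2).** Next come "The complete adverse event investigation form shall be faxed to the sponsor within 24 hrs" and "Within ten days the Sponsor will report to the IRB and the FDA". Neither sentence states which events it covers.
- **Investigator to IRB (14.2).** The investigator sends a copy of the form "to the IRB when events are judged to be serious, unanticipated and (possibly) device related", which is the same three-part limit.
- **Termination (14.2).** "Any serious device related adverse event will lead to the immediate termination of the trial". This sentence does not ask whether the event was anticipated.
- **Suspension or termination (14.3).** The trial can be halted "if the serious adverse device effects are considered disproportionately large compared to the possible benefits of the intervention". Again nothing restricts this to unanticipated effects. The sponsor or principal investigator, the IRBs and the regulators are named as able to decide on continuation.
- **Definitions (14.1).** A serious adverse device effect is defined without regard to anticipation. An anticipated one is a class of its own: it "is an effect which by its nature, incidence, severity or outcome has been identified in the risk management for the device".
- **Routine contact (8.7).** The monitor and the local investigator "will maintain communication on a minimum biweekly basis".

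**The concern.** The events a site must report urgently are fewer than the events on which the plan may stop the trial. Suppose a site sees a serious device effect, finds it in the hazard analysis and follows the telephone sentence literally. It owes no urgent call, yet the same section says that the event ends the trial, and 14.3 counts it in the weighing of harm against benefit.

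At stake is whether the sponsor learns in time of every event that its own stopping provisions rely on. Section 8.1 names three sites, so one site's knowledge does not by itself alert the sponsor or the other two. Section 6 states that no clinical data exist for this device. By contrast, 11.2 requires a protocol deviation made without prior approval to reach the sponsor within 24 hours of the local investigator's knowledge. A foreseen but serious device effect has no equally clear clock.

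**Working it through.** No formula applies to the main point. The check sets the event class behind each reporting step beside the class behind each stopping provision, then looks for another prompt route.

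**Step 1. Scope of each provision**

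| Provision | Unanticipated serious device effect | Anticipated serious device effect |
|---|---|---|
| Telephone report to sponsor (14.2) | Yes, as soon as possible | No |
| Form to sponsor (14.2) | Yes, 24 hours | Unclear; the natural reading is no |
| Sponsor report to IRB and FDA (14.2) | Yes, ten days | Unclear; the natural reading is no |
| Investigator's copy to IRB (14.2) | Yes | No |
| Termination sentence (14.2) | Covered | Covered |
| Weighing against benefit (14.3) | Covered | Covered |

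The right-hand column falls under both stopping provisions and under no clearly stated prompt report. That is so whichever stopping provision prevails.

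**Step 2. Other routes for an anticipated serious device effect**

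- 14.2, opening sentence: adverse events and device deficiencies go to the competent authority under national guidelines. No time limit is stated, and neither the sponsor nor the IRB is named as recipient.
- 14.2, second paragraph: device-related events are all to be investigated. No reporter, recipient or deadline is given.
- 8.6: the sponsor's principal investigator looks into possible vigilance cases and SAEs, but no step says how or when the site informs that person. The local investigator's listed duties include no adverse event reporting.
- 8.7: monitor and site are in regular contact. The contact is not tied to adverse events.
- 7: side effects are to be documented, with no reporting step.
- 12: general compliance with ISO 14155 is promised, but the protocol text sets no clock from it.

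None of these is a stated prompt route to the sponsor.

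**Step 3. Possible delay, as an illustration only**

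The only contact interval in the text that might catch such an event is the biweekly one. The documents do not define the word.

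- Every two weeks: 2 × 7 = 14 days.
- Twice a week: 7 / 2 = 3.5, so 3 to 4 days.

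The stated frequency is a minimum, so contact may be more frequent. It also has no adverse event agenda, so 14 days is not a guaranteed ceiling.

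**Step 4. Dependence of the urgent route on the missing information**

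Under 14.1 an effect can be unanticipated because of its degree of incidence. A single site cannot judge incidence across three sites. The sponsor can do so promptly only if it hears promptly of the anticipated events too.

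**The case against.** The strongest reply has five parts.

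1. **The 24-hour form may be wider.** Its sentence names no event class, and the paragraph opens by saying that all device-related events are investigated. The form could therefore belong to any of them, and on that reading the 24-hour gap closes. This stands as an ambiguity. The sentence follows directly on one limited to unanticipated events, so the narrow reading is the more natural. A site should not have to choose.
2. **Immediate termination presupposes notice.** A site reading 14.2 as a whole would hardly hold such an event for a routine call. That is plausible, but the notice is then implied, while the explicit instruction points the other way.
3. **Regulators do have a route.** A reader might infer that nobody who decides on continuation would hear of the event. The documents do not support that: regulators are among the deciders in 14.3 and receive adverse events under national guidelines, though without a stated time. If principal investigator in 14.3 means the site investigator, that person may also know already. The gap is in prompt notice to the sponsor and, separately, in notice to the IRB.
4. **14.3 does not act on each event.** It allows a discretionary judgement on the effects taken together. This is correct. It still needs a complete and timely count.
5. **Some material cannot be seen.** Part of the text between 14.2 and 14.3, the hazard analysis and the investigator's brochure were not available for this check. The conclusion is limited accordingly.

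The exempt class may also be narrow, because a listed harm that proves worse or more frequent than foreseen becomes unanticipated under 14.1. That limits how often the gap matters but does not remove it.

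**Conclusion.** The mismatch in scope holds. The telephone report, and on its natural reading the 24-hour form, leave out anticipated serious device effects, while both stopping provisions include them. In the visible text such an effect has no clearly stated prompt route to the sponsor. This is more than missing detail, because following the stated rule literally could delay notice of an event that the same section says ends the trial.

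The size cannot be calculated from the documents. The 3 to 14 days rests on two readings of an undefined word and on no contact between routine calls.

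Three stronger conclusions are tempting and are not supported:

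- **A fixed 14-day delay.** The protocol sets no such interval for adverse events.
- **That the omitted harms are the likeliest to occur.** The expected incidences are in the hazard analysis, which was not available.
- **A particular number of subjects exposed meanwhile.** That depends on device supply, timing and uptake of the optional extension.

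The conclusion assumes that the unavailable text contains no wider reporting rule. It does not bear on the endpoints or their analysis.

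**What to change.** In 14.2:

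- State that the telephone report and the 24-hour form to the sponsor apply to every serious and possibly device-related event, whether or not it was anticipated. The sponsor then learns of every event covered by the stopping provisions.
- Unanticipated may remain the condition for the ten-day report to the IRB and FDA. If so, add how the IRB learns of the other serious device effects that count under 14.3. Without that addition, the change reaches the sponsor but not the IRB.

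Separately, the mandatory termination sentence in 14.2 and the discretionary one in 14.3 contradict each other and must be reconciled. The reporting change does not choose between them and is needed under either.

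The cost is a short edit to 14.2, matching site training, and a few more calls and forms in a trial of 15-18 subjects.

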## 14.3 Suspension or premature termination of the clinical investigation

The sponsor/principal investigator, the IRBs, and the regulatory authorities can decide about investigation continuation. The clinical investigation can be suspended or prematurely terminated if the serious adverse device effects are considered disproportionately large compared to the possible benefits of the intervention. If the investigation is terminated or suspended all participants will be informed and appropriate follow-up will be assured. If sponsor/principal investigator terminates or suspends the investigation the relevant IRBs regulatory authorities will be provided with a detailed written explanation of the termination or suspension.

The sponsor/principal investigator can upon completion of the analysis of the reason(s) for a suspension decide to lift the suspension, when the necessary corrective actions have been implemented. The investigators, IRBs, and relevant regulatory authorities will be notified and provided with the relevant data supporting the decision.

